### **5.5 Subgroup analysis**

The descriptive statistics and the analysis related to primary endpoints will be presented separately for adults and pediatric populations. Owing to small sample size, these results will be considered exploratory.

### **5.6 Safety Analysis**

Adverse events (AE) constitute any untoward or unfavorable occurrence in a research participant associated with the participant's involvement in the research that may or may not be related to the individual's participation in research. The adverse events will be collected and coded in accordance with the guidelines specified in MedDRA/CTCAE.

Serious adverse events (SAE) refer to the adverse events that meet at least one of the following criteria:

- Leads to death
- Considered life threatening (putting participants in immediate risk of death)
- Necessitates inpatient hospitalization or prolongation (if already hospitalized)
- Results in persistent or significant disability/incapacity
- Requires medical or surgical intervention to prevent outcomes listed in the above definition of SAE
- Causes significant psychological, social, economic, or legal harm to participants or others
- Results in breach of confidentiality that is damaging to participants' rights, employment, financial standing or reputation

Adverse events will be analysed and listed as per the guidelines listed below:

1. If a participant experiences the same AE multiple times during the study, the patient will be counted only once in the number of participants experiencing the event.
2. If a patient experiences the same AE multiple times but with different severity during the study, the worst or most intense event will be counted.
3. If there are adverse events that are not coded, the summary table will use the exact description from as reported in the database. The statistician may consult with the study investigator for further information to resolve this (i.e. whether it can be reassigned to one of the existing coding)

The safety analysis will be descriptive, and no inferential statistics will be done. Summary statistics will be presented by severity and device relatedness.

### **5.7 Multiple testing**

No adjustment for multiple testing is planned for this pilot study.

### **5.8 Sensitivity analysis**

N/A

### **5.9 Missing data**

There could be missing values from either prototype or commercial device (e.g., Table 4, Ear 1, 2, 3 or Ear 5, 6) or both the devices (e.g., Ear 4). The analysis for all study objectives will be based on complete case analysis (the last column of Table 4 i.e., data available for both devices).

Missing data in the outcome variable arises from inability to take tympanometry measurements for a participant (CNE status), especially for children with the presence of ear pathology, or younger children less likely to sit still for measurements. We will not include an ear in the main analysis if data from one device

(either commercial or prototype) or both devices are missing for that ear. No multiple imputation is planned for this study.

The frequency and proportion of missing data will be presented separately for the prototype and the commercial device. Missing proportions will be compared for commercial and prototype devices by ear status, adults/children, number of ears and tested for statistical significance using either Chi-square test or Fisher's exact test.

Table 4: Example of missing values by device type

	Commercial device	Prototype device	Complete case analysis for all study objectives
Ear 1	✓	missing	
Ear 2	✓	missing	
Ear 3	✓	missing	
Ear 4	missing	missing	
Ear 5	missing	✓	
Ear 6	missing	✓	
Ear 7	✓	✓	✓
Ear 8	✓	✓	✓
Ear 9	✓	✓	✓
Ear 10	✓	✓	✓
...Ear 60			

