### 2.2 Power and Sample size

A sample size of 30 participants (60 ears), with an assumed prevalence of 0.20 will yield a half-width of 95% confidence interval ranging from 0.25-0.33 when the sample sensitivity is 0.80; and a half-width of 95% confidence interval ranging from 0.12-0.18 when the sample specificity is 0.80. The range of the half-width of 95% confidence interval reflect the extreme scenario of the intra-class correlation ranging from 0 to 1.

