### 4 Outcomes, Exposures, and Additional Variables of Interest

#### 4.1 *Outcome(s)*

Table 2. Description of outcome variables

Outcome	Description	Variables and Source	Specifications
Primary Outcome(s)			
Categorical classification of tympanogram types A, B, C  1) Audiologist's interpretation of commercial device versus audiologist's interpretation of prototype device  2A) Audiologist's interpretation of prototype device versus machine learning algorithm's interpretation of prototype device  2B) Audiologist's interpretation of commercial device versus machine learning algorithm's interpretation of prototype device	Tympanograms can be classified into types (Type A, B, C) that help to determine if an eardrum has fluid behind it, is retracted, or perhaps has a perforation, all common ear disease states. Type A indicates normal ear function, and types B and C indicate abnormal middle ear function.	Audiologist commercial device classification (left, right): Tymp_type_au_com_l; Tymp_type_au_com_r  Audiologist prototype device classification (left, right): Tymp_type_au_proto_l; Tymp_type_au_proto_r  Machine learning algorithm prototype device classification (left, right): Tymp_type_ml_proto_l; Tymp_type_ml_proto_r  Forms: 1) Data collection form: Audiologist interpretation and performance for mHealth tympanometer  2) Data collection form: Audiologist interpretation and performance for commercial tympanometer  3) ML Algorithm Interpretation form	1=A; 2=B; 3=C; 4=CNE (could not evaluate)
Secondary Outcome(s)			
Ear canal volume, static admittance and	Numerical measures	Commercial device (left, right):	Numerical measures

tympanometric peak pressure	Commercial device versus prototype device	
ecv_com_l; sa_com_l; tpp_com_l; ecv_com_r; sa_com_r; tpp_com_r
 
Prototype device (left, right): ecv_proto_l; sa_proto_l; tpp_proto_l; ecv_proto_r; sa_proto_r; tpp_proto_r
 
Forms: 1) Data collection form: Audiologist Interpretation and Performance for commercial tympanometer  2) ML Algorithm Interpretation form

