## 6 Limitations

Missing data are more likely to occur for ears that have presence of pathology, because it is potentially more difficult to obtain a reading from a diseased ear. We may also find missingness for children who have higher rates of ear disease and can be more difficult to test. We may over or underestimate the level of agreement between the two devices especially for the ears with pathology.

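### Ears typed by the commercial device but unreadable on the prototype enter no accuracy estimate, and no planned analysis shows how far they could move sensitivity or specificity

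*SAP*

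**What the plan says.** SAP 5.9: "The analysis for all study objectives will be based on complete case analysis". The exclusion sentence begins "We will not include an ear in the main analysis if data from one device" and goes on to cover either device or both. No multiple imputation is planned. In Table 4, Ears 1 to 3 have a commercial result and no prototype result, and they fall outside the complete-case column.

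The protocol (Study Population; Study Stopping/Pausing; Data Analysis) keeps enrolment open until 40 adult and 20 pediatric ears have data from both devices, so ears without a reading are replaced.

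SAP 5.3 takes the commercial type as the reference standard. It estimates sensitivity and specificity on A versus B/C and adds a three-by-three matrix. Neither layout has a place for CNE, although SAP Table 2 records it as code 4.

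On missing readings, SAP 5.9 adds: "The frequency and proportion of missing data will be presented separately for the prototype and the commercial device". It also compares missing proportions by ear status, by adults versus children and by number of ears. SAP 6 warns: "Missing data are more likely to occur for ears that have presence of pathology, because it is potentially more difficult to obtain a reading", and then: "We may over or underestimate the level of agreement between the two devices especially for the ears with pathology". The section headed "5.8 Sensitivity analysis" contains only N/A.

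**The concern.** Objectives 1 and 2B ask for preliminary accuracy of the prototype against the commercial device, and SAP 1.1 says the results will guide design changes before large validation studies. An ear that the commercial device can type and the prototype cannot read bears directly on that question. Under SAP 5.9 it leaves both the numerator and the denominator of accuracy, and replacement then brings the count back to 60 complete ears.

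Accuracy given a reading, shown beside failure rates, is a coherent quantity. What is missing is any planned statement of how much that accuracy could change if the unread ears were counted. The SAP names the possible bias, in either direction, but plans nothing to show its size. The confidence interval around the complete-case estimate reflects sampling error among ears that were read, so it does not include this bias.

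**Working it through.** **Inputs.** 60 ears, "with an assumed prevalence of 0.20" (SAP 2.2), so 0.20 × 60 = 12 diseased and 48 normal ears. Sample sensitivity and specificity are 0.80 (SAP 2.2). The number of ears with a commercial type but no prototype reading is not in the documents, so the counts k (diseased) and m (normal) below are assumptions.

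**Step 1: the plan's own precision.** The SAP names no interval method. An exact (Clopper-Pearson) interval with x = 0.8n comes close. An intra-class correlation of 1 halves the effective number of ears.

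| Quantity | n (correlation 0; 1) | Computed half-width | SAP 2.2 |
|---|---|---|---|
| Sensitivity | 12; 6 | 0.244; 0.331 | 0.25 to 0.33 |
| Specificity | 48; 24 | 0.121; 0.173 | 0.12 to 0.18 |

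All four agree within 0.01. The stated precision therefore corresponds to 60 ears read by both devices. It is not in error, and it makes no allowance for unread ears.

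**Step 2: which ears are affected.**
- Commercial type present, prototype CNE (Table 4, Ears 1 to 3): a reference exists, but the ear is dropped. This is the gap.
- Commercial type absent (Table 4, Ears 4 to 6): there is no reference, so no accuracy estimate could use the ear.
- Both devices read, machine-learning (ML) CNE only: complete under SAP 5.9, which defines completeness by device, so the ear stays in Objective 1. Its handling under Objective 2B is not stated.

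**Step 3: bounds for sensitivity.** With c correct among n complete diseased ears and k unread diseased ears:
- worst case (all CNE incorrect) = c/(n + k)
- best case (all CNE correct) = (c + k)/(n + k)
- distance between them = k/(n + k)

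With n = 12 and c = 0.80 × 12 = 9.6:

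| k | Worst case | Best case |
|---|---|---|
| 1 | 9.6/13 = 0.738 | 10.6/13 = 0.815 |
| 2 | 9.6/14 = 0.686 | 11.6/14 = 0.829 |
| 3 | 9.6/15 = 0.640 | 12.6/15 = 0.840 |

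In whole ears, 10/12 = 0.833 with one unread diseased ear becomes 10/13 = 0.769 to 11/13 = 0.846.

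**Step 4: bounds for specificity.** With n = 48 and c = 0.80 × 48 = 38.4:

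| m | Worst case | Best case |
|---|---|---|
| 1 | 38.4/49 = 0.784 | 39.4/49 = 0.804 |
| 3 | 38.4/51 = 0.753 | 41.4/51 = 0.812 |
| 5 | 38.4/53 = 0.725 | 43.4/53 = 0.819 |

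**Step 5: more diseased ears.** With 24 diseased ears, c = 19.2 and k = 3, the range is 19.2/27 = 0.711 to 22.2/27 = 0.822, narrower than with 12.

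**Step 6: comparison with the planned precision.** The largest sensitivity shift in Step 3 is 0.80 − 0.64 = 0.16, below 0.25. The largest specificity shift in Step 4 is 0.80 − 0.725 = 0.075, below 0.12. These are simple ear-level proportions; the planned GEE may weight ears a little differently.

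**The case against.** The case for leaving the plan as it is has real substance. For the prototype the rule is already fixed: exclusion, no imputation. Missingness is to be reported by device and compared by ear status and by adults versus children, and SAP 6 discloses possible bias in both directions. The objectives seek preliminary estimates in a pilot, and SAP 5.3 plans no test against the hypothesised 80%. The causes that the documents name (a draining ear, a child who will not sit still, pathology) could defeat both devices at once, and such an ear has no reference anyway. The number of prototype-only failures may be close to zero.

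Most of this stands, and it limits the weight of the point. It does not remove it. Missing proportions for each device do not give the joint count needed, because an ear missing on both devices also counts as a prototype failure. The SAP does not say whether ear status in that comparison means the commercial type. If it does, a reader could approximate the bounds; if not, they could not. The words main analysis in SAP 5.9 suggest a second analysis, but none is defined. The table shells (SAP 7.1) are a separate document not available here. If they already show a CNE row, only the bounds and the SAP 5.8 text are outstanding.

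Three stronger readings are tempting and not supported:
- A reader might infer that ML failures also drop out of every accuracy estimate. SAP 5.9 defines completeness by device, so they do not drop out of Objective 1.
- A reader might infer that the prototype CNE rule is open to choice after the data are seen. It is already specified.
- A reader might take 40 consented people for 60 complete ears as a ceiling of 20 prototype failures. The 40 is an anticipated figure, the surplus covers failures on either device, and the documents do not support spreading it at a prevalence of 0.20.

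**Conclusion.** The point holds as a gap in supporting analysis; a reader might infer an error in the main analysis, and the documents do not show one. Ears with a commercial type and a prototype CNE are left out of all sensitivity and specificity estimates, the SAP expects missingness to depend on pathology, and no planned analysis shows the consequence for accuracy. How an ML CNE is treated under Objective 2B is also unstated.

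On the assumed counts, one to three unread diseased ears beside 12 complete ones allow sensitivity to fall by 0.06 to 0.16 or rise by 0.02 to 0.04 from 0.80. This is smaller than the planned half-width but additional to it. The figures rest on SAP 2.2's prevalence and accuracy and on failure counts that the documents do not supply. The bounds are extremes and not expected values.

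**What to change.** Keep the complete-case analysis as the main analysis. Replace N/A in SAP 5.8 with a prespecified sensitivity analysis of all attempted ears that have a commercial type A, B or C, including those later replaced:

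1. Cross-tabulate against the commercial type with prototype CNE as its own row. For Objective 2B, do the same with ML CNE, and state how it is handled in the main 2B estimate.
2. Give sensitivity and specificity with all CNE counted as incorrect and with all CNE counted as correct.
3. Keep replaced ears, with their commercial type, in the dataset transferred to the statistician.

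The cost is one extra table and a short paragraph, using a code that is already collected. The downside is that the bounds may be wide with about 12 diseased ears and may look less favourable than the complete-case figures.

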**Objective 2A:**

To obtain preliminary estimates of the agreement between audiologist's interpretation of the prototype device and machine learning algorithm's interpretation of the prototype device.

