**Agreement between audiologist's and machine learning algorithm's interpretation of the tympanometric tracing types (based on prototype device):** The agreement between audiologist's and machine learning algorithm's interpretation of the tympanometric tracing (based on prototype device) will be tested for statistical significance using Durkalski's adjustment to the McNemar's test statistics for the analysis of clustered matched-pair data (Durkalski et al). Durkalski's method for the analysis of clustered matched-pair data will maximize the use of available data and adjusts for multiple units within a cluster while avoiding any assumptions related to intra-cluster correlation. The Kappa statistic and the corresponding 95% confidence interval will be estimated using cluster-bootstrapped approach (Kang et al). The bootstrapped approach will ensure maximal data usage while also taking into account the potential subject-level clustering. The aforementioned measures of agreement will be based on a 3-level outcome.

**Diagnostic accuracy of the prototype device based on machine learning algorithm's interpretation:** The diagnostic accuracy of the prototype device (based on machine learning algorithm's interpretation) will be estimated using sensitivity and specificity. These estimates will be obtained using the analysis approach described earlier for diagnostic accuracy of prototype device based on audiologist's interpretation. The secondary analysis of diagnostic accuracy as well as the analysis based on 3-level outcome will be done using the approach described earlier for the prototype device based on audiologist's interpretation.

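### The both-devices complete-case rule in SAP 5.9 also governs Objective 2A, which uses no commercial data, so usable prototype-only ears are dropped (minor)

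*SAP*

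**What the plan says.** SAP 5.9 sets one rule for everything: "The analysis for all study objectives will be based on complete case analysis". It identifies the complete cases as "the last column of Table 4 i.e., data available for both devices" and repeats the exclusion: "We will not include an ear in the main analysis if data from one device" (commercial or prototype) or from both is missing. It foresees ears with only one device's result ("e.g., Table 4, Ear 1, 2, 3 or Ear 5, 6"). In Table 4, Ears 5 and 6 have a prototype result and no commercial one, and the complete-case column, which is headed as covering all objectives, is blank for them.

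Objective 2A, under the primary Objective 2 in SAP 1.3, is "To obtain preliminary estimates of the agreement between audiologist's interpretation of the prototype device and machine learning algorithm's interpretation of the prototype device". SAP 4.1 takes the ML result from the prototype alone: "Machine learning algorithm prototype device classification (left, right): Tymp_type_ml_proto_l; Tymp_type_ml_proto_r". The audiologist's reading for this comparison is also the prototype one. The protocol's description of the ML test names raw prototype data as the input and attaches no commercial condition.

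No other section exempts 2A. SAP 3 has a single analysis population, participants who were given both devices. SAP 5.8 lists no sensitivity analysis. The reference in SAP 5.9 to a main analysis hints at another one, but none is specified.

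**The concern.** A complete-case rule should require the variables an analysis uses. Both-device data are needed for Objective 1 (prototype against commercial), 2B (ML against commercial) and 3 (numerical differences between devices). They are not needed for 2A, where both readers look at one prototype tracing.

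Two things are at stake. First, data already collected for a primary objective are not used. Second, the audiologist-ML kappa becomes conditional on a different device having worked in that ear. SAP 5.9 and SAP 6 link missing readings to ear pathology and to young children, so the ears removed may differ from those kept. SAP 6 discusses the consequence only for agreement between the two devices and does not mention audiologist-ML agreement.

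**Working it through.** **No planned figure to reproduce.** Neither document gives a sample size, power or precision for Objective 2A. The interval half-widths in SAP 2.2 concern sensitivity and specificity. The kappa power in the protocol's Data Analysis section concerns agreement between devices.

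**Step 1: apply the rule to Table 4.** Of the ten ears filled in, both devices gave data in Ears 7–10 (4 ears) and the prototype gave data in Ears 5–10 (6 ears). The rule removes 6 − 4 = 2 ears that 2A could use, for lack of a commercial reading only. This shows how the rule works; the table is an invented example and gives no rate.

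**Step 2: how many ears could be affected?** The protocol keeps enrolling until 40 adult and 20 pediatric ears have data from both devices, so 60 both-device ears remain for 2A. It expects to consent no more than 40 people, that is 80 ears. Incomplete ears of every kind are then at most about 80 − 60 = 20, and prototype-only ears are a subset. Their number is not given, so I take 0 to 20 as an assumed range.

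**Step 3: precision.** Assumptions: true kappa κ = 0.80, independent ears, and the same category shares *m* for both readers, with cell probabilities p_ij = (1 − κ)m_i m_j, plus κm_i on the diagonal. The large-sample (Fleiss–Cohen–Everitt) standard error per ear is

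s = √{ Σ p_ii[1 − (p_i. + p_.i)(1 − κ)]² + (1 − κ)² Σ_{i≠j} p_ij(p_.i + p_j.)² − [κ − p_e(1 − κ)]² } / (1 − p_e),

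and the half-width is 1.96·s/√n. This gives s = 0.733 for an A/B/C mix of 80/10/10 and s = 0.510 for equal thirds.

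| Ears in 2A | 80/10/10 | Equal thirds |
|---|---|---|
| 60 | 0.185 | 0.129 |
| 60 + 2 | 0.182 | 0.127 |
| 60 + 10 | 0.172 | 0.119 |
| 60 + 20 | 0.161 | 0.112 |

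The largest difference is 0.185 against 0.161: 0.024 between the rounded values, about 0.025 before rounding. Allowing for correlation between ears would change the levels, but not the conclusion that a modest number of added ears changes precision little.

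**Step 4: selection, raw agreement.** Suppose, as an assumption, that the 60 complete ears agree 90% (54 ears) and the dropped ears would agree 50% to 70%.

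- 10 dropped ears: (54 + 5)/70 = 84.3% to (54 + 7)/70 = 87.1%.
- 2 dropped ears: (54 + 1)/62 = 88.7% to (54 + 1.4)/62 = 89.4%.

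**Step 5: selection, kappa.** Kappa also depends on the category mix, so lower raw agreement in the dropped ears need not mean lower kappa. Take 60 ears that both readers split 48/6/6, with 54 agreeing. Then p_e = (48² + 6² + 6²)/60² = 0.66 and κ = (0.90 − 0.66)/0.34 = 0.71. Add six abnormal ears, so that the readers' totals become 48/10/8 and 48/9/9. Then p_e = (48·48 + 10·9 + 8·9)/66² = 0.566.

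- 5 of the 6 agree: observed agreement 59/66 = 0.894, κ = (0.894 − 0.566)/0.434 = 0.76. Agreement falls and kappa rises.
- 3 of the 6 agree: observed agreement 57/66 = 0.864, κ = (0.864 − 0.566)/0.434 = 0.69. Both fall.

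Either direction is possible.

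**The case against.** The best defence is that a common ear set is a reasonable choice. The commercial device is the reference standard, and one set lets audiologist accuracy, ML accuracy and audiologist-ML agreement be read on the same ears. It also matches the protocol's rule that an ear is complete when both devices gave results. This stands as a reason to keep the both-device result for 2A as a supporting analysis. The SAP does not offer that reason, and it is no ground for making that set the only one.

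Four stronger readings are tempting, and the documents do not support them.

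- *SAP 5.9 contradicts SAP 5.3*, which says "The bootstrapped approach will ensure maximal data usage while also taking into account the potential subject-level clustering". In context this is about using both ears of a participant despite clustering; it does not address ears that lack a device.
- *A third of the 2A data is lost.* The 2 of 6 ears come from an illustrative table. The documents give no rate of commercial-only failure, and their own example of a failed reading, a draining ear that prevents a seal, could affect both devices.
- *The 2A sample falls short of 60.* Replacement prevents this.
- *Kappa is overstated.* A failed commercial reading does not show that the prototype tracing was ambiguous, SAP 6 itself allows error in either direction for device agreement, and Step 5 shows kappa can move either way.

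**Conclusion.** The point holds as a minor one. On its plain text SAP 5.9 drops from Objective 2A ears that have everything 2A needs, and nothing elsewhere in the plan restores them. The number of such ears is unknown. The loss of precision is small: at most about 0.025 on the half-width under the assumptions of kappa 0.80, independent ears and 20 dropped ears, which is the ceiling for incomplete ears of all kinds. Replacing incomplete ears restores the count but not the mix, since each replacement must also be readable on both devices. Some selection is therefore possible, given the link the SAP draws between missing readings, pathology and young age. Its size and its direction for kappa cannot be derived from the documents.

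**What to change.** - **SAP 5.9:** define evaluable ears by objective. Keep the both-device rule for Objectives 1, 2B and 3. For 2A, include every ear whose prototype tracing has an A, B or C result from both the audiologist and the ML algorithm (could-not-evaluate codes excluded), whether or not a commercial reading exists.
- **Table 4:** replace the single complete-case column with one per objective, with Ears 5 and 6 marked as available for 2A, provided both readers classified the tracing.
- **SAP 3:** let participants who were not tested with the commercial device enter 2A. The present population keeps someone whose commercial test was tried and failed, but excludes someone who never had it, so changing 5.9 alone would leave that group out.
- **Supporting analysis:** report 2A on the both-device subset as well, which preserves the comparison on common ears.

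The cost is SAP wording and one extra run of the 2A analysis. No new data are collected. The 2A and 2B denominators may differ slightly, so each table should state its number of ears and participants.

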Analyses for the pilot validation will include: 1) comparison of categorical classifications of tympanogram types for the commercial vs prototype devices; 2) evaluating potential intra-participant correlation between ears; 3) assessing differences in numerical measures between the commercial and prototype tympanometer; and 4) evaluating performance of mHealth tympanometer and commercial tympanometer.

- 1) For each device, commercial and prototype, tympanograms will be categorized into one of 3 categories: A, B and C. To assess the agreement between the two devices with respect to categories, Bowker's test of symmetry and the Kappa coefficient conventional methods to assess agreement, will be used. For the initial analysis, both tympanograms will be performed for each ear and no adjustments will be made for participants (i.e., most will have both ears included).
- 2) To assess the potential effect of participant and ear status (normal, diseased) for participants where both ears are included, each participant's ears will be characterized as (both normal, both diseased, one diseased and one normal). Within those categories, the number of ears for which there is concordance between the two tympanograms for each participant will be 0, 1 or 2. Pearson's chi-square test will be used to compare the three groups defined by ear status with respect to the distributions of the number of ears with concordance.
- 3) The Wilcoxon signed rank test will be used to determine if the differences in the numerical measures (ear canal volume, static admittance and tympanometric peak pressure) obtained from the commercial and prototype devices are significantly different from zero. No adjustment for multiple testing is planned.
- 4) Audiologist assessment of the mHealth and commercial tympanometers will be captured through questionnaires which assess 4 performance measures using a 5-point Likert scale. For each performance measure, the Kappa coefficient and Bowker's test of symmetry will be used to assess agreement between the two mHealth and commercial tympanometers with respect to responses.

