### 5.3 Analysis of Primary Endpoints

The primary outcome is the classification of the tympanogram types, which can be categorized into one of the three categories A, B, and C. The classification of tympanogram types from the commercial device (based on audiologist's interpretation) will be considered as reference standard (gold standard). In the subsequent section, the unit of cluster will refer to subjects who contribute to tympanogram types for left and right ears using the prototype as well as the commercial device. The analysis will be done based on a 2-level outcome, namely A (normal) vs B/C (diseased).

Diagnostic accuracy of the prototype device based on audiologist's interpretation: The diagnostic accuracy of the prototype device (based on audiologist's interpretation) will be estimated using sensitivity and specificity. The sensitivity and specificity will be estimated using a binary outcome – A (normal) vs B/C (diseased). To ensure the maximum use of the available data, the estimates of sensitivity and specificity will

be computed at ear-level. Taking into consideration the potential correlation between the two ears, the sensitivity and specificity will be estimated using generalized estimating equation (GEE), with a robust (sandwich) variance estimator and unstructured correlation matrix.

**Secondary analysis of primary endpoints:** The secondary analysis of primary endpoints will constitute additional measures of diagnostic accuracy namely – positive predictive value (PPV), negative predictive value (NPV), positive likelihood ratio (PLR), and negative likelihood ratio (NLR). To obtain estimates of PPV and NPV, the disease prevalence will be set at 0.20 (estimate of disease prevalence may be updated).

**Analysis based on 3-level outcome:** The performance of the prototype device will be presented using a three-by-three confusion matrix. The overall accuracy will be computed from the confusion matrix. We will also compute separate estimates of sensitivity and specificity separately for tympanometric tracing types B and C respectively.

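### SAP 5.9 tests missing readings with chi-square or Fisher's exact test, which ignore that each ear is tried with both devices and that most people contribute two ears

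*SAP*

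**What the plan says.** SAP 5.9 restricts every objective to ears with a reading from both devices and rules out multiple imputation. For the excluded readings it plans two outputs. The first is descriptive: "The frequency and proportion of missing data will be presented separately for the prototype and the commercial device". The second is inferential: "Missing proportions will be compared for commercial and prototype devices by ear status, adults/children, number of ears", with the proportions "tested for statistical significance using either Chi-square test or Fisher's exact test". SAP 5.8 plans no sensitivity analysis, so the second output is the only formal analysis of failed readings.

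Four other places bear on it:

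- **Design.** SAP 2.1 and Protocol, Study Design and Procedures: the audiologist tests each ear with the prototype and then with the commercial device. Table 4 of the SAP is laid out the same way, one row per ear and one column per device.
- **Test used elsewhere.** SAP 5.3 applies Durkalski's clustered version of McNemar's test to audiologist v algorithm, because ears are matched and nested in people.
- **Normal and diseased.** SAP 5.3 calls type A normal and B/C diseased, with the commercial reading as reference. In SAP 4.1, could-not-evaluate (CNE) is a fourth code of that same variable. The Protocol's Data Analysis section uses *ear status* with the levels normal and diseased but does not say where the label comes from.
- **Otoscopy.** SAP 4.2 records otoscopy for each ear, with codes for normal, named pathologies and could not evaluate. The SAP does not link it to *ear status*.

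**The concern.** SAP 6 names missing readings in pathological ears as a limitation that could bias agreement in either direction. The study is a first-in-human pilot meant to guide design changes. Whether the prototype fails more often than the reference device, and in which ears, is therefore a central feasibility question, and SAP 5.9 is where it would be answered.

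The sentence can be read as device v device, or as subgroup v subgroup within each device. The named tests do not fit either reading. On the first, a real excess of prototype failures could be missed. On the second, a difference between adults and children could be declared too readily.

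A secondary difficulty is that *ear status* is a stratifier with no definition. The only normal/diseased rule in the SAP depends on a reading that some of these ears do not have.

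**Working it through.** The documents give no expected missing rate, power or margin for this comparison, so there is no planned figure to reproduce. The rates and correlations below are assumptions. The sample sizes come from the documents: up to 40 people consented, so 40 × 2 = 80 ears attempted (Protocol, Data Analysis), and a target of 40 adult and 20 pediatric ears. Alpha is two-sided 0.05 (SAP 5.1).

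**1. Device v device.** Let the prototype miss a proportion p₁ and the commercial device p₂, with within-ear correlation φ. The proportion of ears missed by both is

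p₁₁ = p₁p₂ + φ√[p₁(1−p₁)p₂(1−p₂)].

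With p₁ = 0.20, p₂ = 0.10 and φ = 0.5: p₁₁ = 0.02 + 0.5 × 0.12 = 0.08. Prototype-only failures are 0.20 − 0.08 = 0.12 and commercial-only failures 0.10 − 0.08 = 0.02.

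- True variance of the difference: (0.12 + 0.02 − 0.10²)/80 = 0.13/80.
- Variance if the two sets of readings were independent: (0.16 + 0.09)/80 = 0.25/80.

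The unpaired formula overstates the variance almost twofold. At φ = 0 the true value is (0.18 + 0.08 − 0.01)/80 = 0.25/80, so nothing is lost.

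Normal approximation to power at φ = 0.5:

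- Unpaired chi-square, pooled proportion 0.15: (0.10 − 1.96√(2 × 0.1275/80)) / √(0.13/80) = −0.26, power about 0.40.
- McNemar: (0.10√80 − 1.96√0.14) / √0.13 = 0.45, power about 0.67.

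Simulation (20,000 runs, 80 ears, 20% v 10% missing) agrees:

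| φ | Chi-square | Fisher | McNemar, asymptotic | McNemar, exact |
|---|---|---|---|---|
| 0 | 0.42 | 0.34 | 0.43 | 0.34 |
| 0.3 | 0.40 | 0.32 | 0.55 | 0.45 |
| 0.5 | 0.38 | 0.29 | 0.70 | 0.60 |

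With both devices at 15% missing, 60 ears and φ = 0.5, simulated type I error is 0.008 (chi-square), 0.002 (Fisher), 0.048 (asymptotic McNemar) and 0.019 (exact McNemar). The unpaired tests are well below the nominal 0.05.

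These runs treat ears as independent of one another. They isolate the effect of pairing and are not the power of the clustered test.

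**2. Adults v children within one device.** Each person's two ears fall in the same group, so the variance is inflated by 1 + (2 − 1) × ICC. At ICC 0.5 the factor is 1.5, the effective critical value is 1.96/√1.5 = 1.60, and the two-sided error is about 0.11. Simulation with 20 adults and 10 children at 15% missing gives:

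| ICC | Chi-square | Fisher |
|---|---|---|
| 0 | 0.045 | 0.036 |
| 0.5 | 0.108 | 0.087 |
| 1 | 0.156 | 0.126 |

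For normal v diseased ears the same inflation arises where both ears of a person share a status. Where a person has one ear of each status, positive correlation works the other way.

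**3. Ear status, using Ears 1–10 of the SAP's illustrative Table 4.** The commercial reading is missing in 3/10 (Ears 4–6) and the prototype reading in 4/10 (Ears 1–4). One ear fails on both, three on the prototype only and two on the commercial device only.

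- Status from the commercial reading: Ears 4–6 cannot be classed. Among the seven that remain, commercial missingness is 0/7 by construction and prototype missingness is 3/7.
- Status from whichever reading exists: only Ear 4 is unclassed.
- Status from otoscopy: every ear is classed unless otoscopy itself could not be evaluated.

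**The case against.** A reader might infer that the SAP defines *ear status* from the very tympanogram that is missing, so that commercial missingness is always zero within strata. The documents do not support this. The SAP never defines the term. The A v B/C rule is stated for the accuracy outcome, and SAP 5.9 does not refer to it. Otoscopy per ear is at least as natural a source and may be what was meant. The forced zero holds only if status is taken from the commercial reading alone, and even then Ears 1–3, which lack only the prototype reading, can be classed. What stands is that the term needs a definition.

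A reader might also infer that commercial failures would go unseen. They would not: the missing frequency is reported for each device whatever *ear status* means. Only the view stratified by status is at risk.

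Nor will the unpaired test always hide an excess. Take an assumed 8 v 2 failures in 68 ears, with both commercial failures among the prototype's. Fisher gives p = 0.096 and exact McNemar (6 v 0 discordant) 0.031, but Pearson chi-square, which SAP 5.9 equally allows, gives 0.049. With 9 v 2 nested the same way, the values are 0.055, 0.016 and 0.028. In the 8 v 2 case exact McNemar weakens to 0.070 with one shared failure and 0.109 with none. The argument rests on error rates over a range of correlations, not on one table.

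Finally, the stakes are limited. This is a supplementary analysis in a pilot, SAP 1.1 permits justified deviations, and the table shells are in a separate document that may specify more. All of that stands and bears on priority. It does not make the named tests fit the data.

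**Conclusion.** The concern holds in this form: SAP 5.9 applies tests for independent observations to data that are paired by ear and clustered by person, and on either reading of the sentence the error rates are not the nominal ones.

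For device v device the direction is conservative, with a loss of power from about 0.70 to 0.38 under the assumed 20% v 10% missing, 80 ears and φ = 0.5. The loss shrinks at φ = 0.3 and vanishes at φ = 0. Positive correlation is plausible, since the Protocol's own example of a failed tracing, a draining ear that prevents a seal, would affect either device. For adults v children within a device the direction is anti-conservative, about 0.11 instead of 0.05 for chi-square at an assumed ICC of 0.5.

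The *ear status* point is a clarification of an undefined term, not a demonstrated circular definition. No primary or secondary estimate changes. The change is still worth making, because this is the only formal analysis of device failure.

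**What to change.** In SAP 5.9:

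1. State which contrasts are intended: device v device, subgroups within a device, or both.
2. For device v device, tabulate ears that failed on the prototype only, on the commercial device only, on both and on neither. Test with the Durkalski-adjusted McNemar statistic already in SAP 5.3. A plain McNemar test would handle the pairing but not the two ears per person.
3. For subgroup contrasts within a device, use a cluster-adjusted test, for example a GEE model for missing/not missing with robust variance by participant.
4. Define *ear status* for this comparison from otoscopy, with could not evaluate as its own row, and use all attempted ears as the denominator.

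The cost is SAP wording and matching table shells. Otoscopy and CNE status are already recorded for each ear, so no new data are needed.
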